11.2 Radiation therapy

Acute toxicities: Nausea with or without emesis is an anticipated side-effect and may be treated with antiemetic medications. Fatigue and a decrease in all blood counts are expected. Patients generally have transient complete alopecia and may have permanent epilation in some regions. Skin erythema is expected but is rarely severe when IMRT is used. Temporary xerostomia and dysphagia as well as diarrhea may occur.

Late effects: The goal of this study is to reduce the incidence and severity of late effects of radiation therapy by reducing the dose of external beam radiation and by treating a focal boost volume using IMRT. Common late effects of radiation for medulloblastoma include neurocognitive dysfunction, growth impairment, hearing loss, and endocrine dysfunction (hypothalamic/pituitary, thyroid, and gonadal). Radiation dose to the gonads may increase the risk of infertility, especially in girls. Rare but severe late effects may include secondary malignancies (approximately 5%) and necrosis of central nervous system tissue, including brainstem and spinal cord (approximately 1-2%).

11.3 Vincristine

IRB
PB

Amended: 2/26/08

Neuromuscular effects, peripheral neuropathy, jaw pain, abdominal pain, mucositis, nausea and vomiting, hypersensitivity, urinary retention, optic atrophy (rare), blindness (rare), constipation, loss of deep tendon reflexes, foot and wrist drop, paresthesia, alopecia, convulsion (rare). Hyponatremia (SIADH). Severe soft tissue damage if extravasated. Vincristine is very irritating and must not be given intramuscularly, subcutaneously or intrathecally. Intrathecal administration of vincristine almost always has resulted in death.

11.4 Lomustine

Myelosuppression. Anorexia, nausea and vomiting, mucosal ulceration. Alopecia. Transient liver function abnormalities. Pulmonary infiltrate and fibrosis. Decreased renal size, progressive azotemia, kidney failure.

11.5 Cisplatin

Myelosuppression. Severe nausea and vomiting. Peripheral neuropathy, seizures, and high frequency hearing loss. Abnormalities in serum creatinine and creatine clearance, renal tubular necrosis, proteinuria, hypocalcemia, hypomagnesemia. Anaphylactic hypersensitivity (tachycardia, wheezing, and hypotension). Optic neuritis, papilledema. Transient liver function abnormalities.

12.0 CRITERIA FOR THERAPEUTIC RESPONSE/OUT COME ASSESSMENT

The study's stopping rule (section 14.0) refers to failures. Failures are defined as unequivocal tumor progression or treatment-associated death. Unequivocal tumor progression may be determined via radiological studies (head or spine MRI) reviewed by the study radiologist or CSF cytology positivity reviewed by the study pathologist. If radiological studies suggest possible, but not unequivocal, progression, biopsy should be strongly considered.

13.0 CRITERIA FOR REMOVAL FROM STUDY

Patients will be removed from the study if grade 4 toxicity due to the test dose of 131-I-3F8 occurs, tumor recurs or progresses post-external beam radiation therapy, if the patient is significantly non-compliant with the treatment plan, if they withdraw consent, or in the event of death.

14.0 BIOSTATISTICS

A total of 20 patients will be enrolled on this pilot study. We have recently seen 3 to 4 patients per year potentially eligible for this study at MSKCC, but it is anticipated that the unique approach proposed in this protocol will allow accrual to be approximately 6 patients per year.

Children with standard-risk medulloblastoma have been reported to achieve 3-year progression-free survival of 86%. Of those who failed, half failed within the first 2 years of diagnosis.² CCG-9961 expanded the approach to a larger group of patients, but outcome data are not yet available. If they become available during the conduct of this trial, the statistical considerations described in this section will be revised if necessary.

We will stop the trial if 6 or more patients fail before 3 years. The likelihood of stopping the trial is only 7% if the true 3-yr PFS is comparable to the control data (85%), and increases to 23% if the true PFS is 75% and to 76% if the true 3-yr PFS is only 65%.

Neuropsychological test results will be reported in tabular format for each evaluation time (baseline, and annual post-treatment), using means and standard deviations or medians and ranges, as appropriate. They will be reported both as raw scores and as age/sex-adjusted "z-scores" and tracked for changes over time relative to baseline. Thus, given the relatively small sample size of 20 patients, the analysis of these scores for evidence of neurotoxicity, or lack thereof, will primarily be descriptive.

Should the results of this trial be encouraging, future possibilities would include use of this strategy on a larger scale through the Children's Oncology Group, and/or additional institutional study of further decrease of the craniospinal RT dose, possibly in conjunction with the use of an increased radioimmunotherapy dose.

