4.0 STUDY DESIGN

This is a single-arm study of post-operative radioimmunotherapy (intrathecal 131-I-3F8), reduced-dose craniospinal radiation therapy (1800 cGy), primary site boost (to 5400 cGy) via IMRT and standard chemotherapy. Statistical stopping rules are defined to minimize the risk of excessive failures. Long-term neuropsychological, neuroendocrine, audiometric and growth parameters will be closely followed to assess long-term morbidities that are hypothesized to be reduced with this regimen.

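### The stopping probabilities in Section 14.0 describe the final failure count; the much lower chance that the rule acts while enrolment is open is not given, and the 75% PFS entry is wrong

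*Combined protocol and SAP*

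**What the plan says.** Section 4.0 gives the purpose: "Statistical stopping rules are defined to minimize the risk of excessive failures". Section 14.0 sets the sample size ("A total of 20 patients will be enrolled on this pilot study") and the rule: "We will stop the trial if 6 or more patients fail before 3 years". Section 12.0 defines the event: "Failures are defined as unequivocal tumor progression or treatment-associated death".

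On performance, Section 14.0 states "The likelihood of stopping the trial is only 7% if the true 3-yr PFS is comparable to the control data (85" (the bracket reads 85%), then 23% at a PFS of 75% and 76% at 65%.

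The inputs that govern timing are in the same section. On accrual: "We have recently seen 3 to 4 patients per year potentially eligible for this study at MSKCC", but the new approach "will allow accrual to be approximately 6 patients per year". On the reference study: "Of those who failed, half failed within the first 2 years of diagnosis".

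Section 14.0 does not say when the count is checked, whether accrual pauses, what stopping entails once everyone is enrolled, or where the 3-year clock starts. Section 13.0 concerns removal of individual patients only.

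**The concern.** A rule meant to contain excess failures limits exposure only if it can act while patients can still be kept off the regimen. Section 11.0 lists more failures, from the lower craniospinal dose and the smaller boost volume, among the possible risks. Whoever weighs that risk needs to know how often the rule would close enrolment early if the regimen were inferior.

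The quoted probabilities do not answer that. They depend only on how many of 20 patients eventually fail, and take no account of entry or failure times. With entry spread over about 3 years and failures counted for 3 years per patient, the two quantities can differ widely. In addition, one of the three figures does not follow from the rule.

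**Working it through.** **Step 1. Reproduce the plan's figures.** With q = 1 - PFS and n = 20, P(X ≥ 6) = 1 - Σ(k=0..5) C(20,k) q^k (1-q)^(20-k).

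| True 3-year PFS | q | Stated | Recalculated |
|---|---|---|---|
| 85% | 0.15 | 7% | 6.7% |
| 75% | 0.25 | 23% | 38.3% |
| 65% | 0.35 | 76% | 75.5% |

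The first and last agree, so the figures are full-sample probabilities with complete 3-year follow-up. The middle one does not agree. A boundary of 7 or more gives 2.2%, 21.4% and 58.3%, so no simple change of boundary recovers all three.

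**Step 2. When the last patient enters.** With even entry, patient 20 enters 19/rate years after patient 1: 19/6 = 3.2 years at 6 per year, 19/4 = 4.8 at 4 per year, and 19/3 = 6.3 at 3 per year.

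**Step 3. Failure timing.** Three patterns were used, each uniform within its periods or constant in hazard:

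- 50/50: half of the 3-year failures in years 0-2 and half in year 3. This reads the Section 14.0 sentence as applying to 3-year failures.
- 75/25: the same sentence read as covering failures to 5 years (an assumption). Section 3.0 gives PFS of 86% at 3 years and 79% at 5 years for the same reference study. Half of the 21 points lost by year 5 is 10.5, and 10.5/14 = 75% of the 3-year failures.
- Constant hazard over 3 years.

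**Step 4. Chance of triggering before patient 20 enters.** At that moment the earlier patients have follow-up f_i = i/rate, i = 1 to 19. Each has a recorded failure with probability q·F(f_i), where F is the share of 3-year failures that have occurred by f_i.

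Hand check for 50/50 at 6 per year: F(f) = 0.25f up to 2 years and 0.5 + 0.5(f - 2) up to 3 years.

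- i = 1 to 12: 0.25 × 78/6 = 3.25
- i = 13 to 18: 4.75
- i = 19: 1
- Sum: 9.0. Expected failures on record at 65% PFS: 0.35 × 9.0 = 3.15, against a boundary of 6. The eventual expectation is 0.35 × 20 = 7.

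Simulation (200,000 trials per cell, even entry, clock from enrolment, failures known at once) gives the chance of a sixth failure before the twentieth entry:

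| Accrual | Pattern | PFS 85% | PFS 75% | PFS 65% |
|---|---|---|---|---|
| 6/year | 50/50 | 0.1% | 1.6% | 7% |
| 6/year | 75/25 | 0.4% | 4.6% | 18% |
| 6/year | constant hazard | 0.3% | 4.1% | 17% |
| 4/year | 50/50 | 0.7% | 7% | 25% |
| 4/year | 75/25 | 1.3% | 12% | 36% |
| 4/year | constant hazard | 1.1% | 11% | 35% |
| 3/year | 50/50 | 1.3% | 12% | 38% |
| 3/year | 75/25 | 2.1% | 17% | 46% |
| 3/year | constant hazard | 1.8% | 16% | 46% |
| Any time | any | 6.7% | 38.3% | 75.5% |

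**Step 5. Share of triggers that come too late to limit entry (PFS 65%).** At 6 per year: 1 - 7.1/75.5 = 91% (50/50) to 1 - 17.7/75.5 = 77% (75/25). At 3 per year: 1 - 38.0/75.5 = 50% to 1 - 46.2/75.5 = 39%. At 6 per year with 50/50, the sixth failure, when it occurs, comes at a median of 4.1 years after first entry, with 19.8 of 20 patients enrolled on average.

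**Sensitivity.** Random (Poisson) arrivals with 50/50 give 9% at 6 per year and 24% at 4 per year. Placing half of the failures in year 1 (an assumption) gives 22%, 40% and 49% at 6, 4 and 3 per year. Delay in recognising failures would lower all of these figures. Starting the clock at diagnosis would raise them slightly.

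**The case against.** The text never says that 76% is the chance of halting enrolment. It speaks of stopping the trial, and a sixth failure after accrual closes still matters: Section 14.0 makes a larger study, or a further cut in craniospinal dose, depend on encouraging results. This stands. The fault is an unqualified label and a missing figure, not a false statement about enrolment.

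A reader might infer that the rule almost always triggers too late and so protects nobody. The documents do not support that. The 6 per year is a hope, and 3-4 per year is what the site had seen. At 3 per year with constant hazard, 45.9/75.5 = 61% of triggers come before the twentieth entry.

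A reader might also take 7% as the single answer at planned accrual. It rests on one reading of an ambiguous sentence about failure timing; the other reading gives 18%. Timing in the reference study need not carry over to a regimen that fails more often.

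Nor can it be asserted that this is the only trial-level rule, because the text between the end of Section 14.0 and Section 15.2 was not available for this review.

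None of this closes the gap: the most favourable case tested is 49%, still well below 76%.

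**Conclusion.** The point holds in limited form. The 7% and 76% are chances of ever reaching 6 failures among 20 patients with full follow-up. The 23% is wrong under that definition and should be 38%. The chance that the rule acts during enrolment is not given. At a true PFS of 65% it is about 7-18% at 6 per year and about 25-46% at 3-4 per year, so roughly three quarters to nine tenths of triggers at planned accrual come after the last entry.

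These ranges rest on even entry, immediate knowledge of failures, a clock starting at enrolment, and the three timing patterns above. The binomial results need none of the timing assumptions. Severity is should-fix: the stated operating characteristics need restating, but the rule is not without effect.

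**What to change.** 1. In Section 14.0, label the figures as the probability that 6 or more of 20 patients fail by 3 years with complete follow-up, and correct the 75% PFS entry from 23% to 38%. Relabelling alone would leave a wrong number under an exact definition. Beside each figure, state the chance of triggering before accrual ends at 6 and at 3-4 per year, with the timing assumption. To make these figures definite, say when failures are counted and where the 3-year clock starts. The cost is wording and a short calculation, with no extra patients or procedures; the stated protection will look weaker.

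2. Optionally, add an accrual-phase review boundary using the Section 12.0 failure definition, for example a pause for review at 4 failures while enrolment is open. At 6 per year with the 50/50 pattern this triggers during accrual in 39% of trials at 65% PFS and 4% at 85%. Across the three patterns, the total chance of any trigger at 85% PFS rises from 6.7% to about 9-11% at 6 per year and about 13-20% at 3-4 per year. The boundary should therefore be calibrated to realistic accrual before it is adopted. Change 1 does not depend on it.

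### The 23% chance of stopping at a true 3-year PFS of 75% does not follow from the stated rule, which gives 38%

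*Combined protocol and SAP*

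**What the plan says.** Section 14.0 sets the sample size: "A total of 20 patients will be enrolled on this pilot study". It sets one stopping boundary: "We will stop the trial if 6 or more patients fail before 3 years". Section 12.0 defines the event that is counted: "Failures are defined as unequivocal tumor progression or treatment-associated death".

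Section 14.0 then gives the chance of stopping at three true 3-year PFS values. It is 7% at 85%, which the plan treats as comparable to the control data. From there it "increases to 23% if the true PFS is 75% and to 76% if the true 3-yr PFS is only 65"%.

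The section names no method for these probabilities. It describes no schedule of interim looks, no smaller evaluable denominator and no allowance for censoring. Section 4.0 describes the purpose of stopping: "Statistical stopping rules are defined to minimize the risk of excessive failures".

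**The concern.** The three probabilities should lie on one curve, because they describe one rule applied to one sample size. The middle one does not. From 85% to 75% PFS the printed probability rises by 16 points (7% to 23%), and from 75% to 65% it rises by 53 points (23% to 76%). A boundary of 6 in 20 does not behave that way over this range.

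This sentence is the plan's only account of how its only stopping rule performs. The 75% row shows what happens if the regimen costs 10 points of PFS against the 85% reference, a loss that matters when craniospinal dose and boost volume are both being reduced. A reader is told that the rule would stop fewer than 1 in 4 such trials, and may judge it weak at that point. Section 14.0 also says the statistical considerations may be revised when results of the larger cooperative-group study arrive, so a wrong figure could carry into that revision.

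**Working it through.** **Inputs, all from Section 14.0**
- Number of patients: n = 20.
- Boundary: r = 6 or more failures before 3 years.
- Failure probability: q = 1 − PFS, so q = 0.15, 0.25 and 0.35.
- Printed stopping probabilities: 7%, 23% and 76%.

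**Assumption.** All 20 patients are enrolled and assessable for failure to 3 years.

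**Formula.** P(stop) = P(X ≥ 6) = 1 − Σ C(20, k) q^k (1 − q)^(20 − k), summed over k = 0 to 5.

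**Step 1: reproduce the two outer figures.**
- q = 0.15: the terms for k = 0 to 5 are 0.03876, 0.13680, 0.22934, 0.24283, 0.18212 and 0.10285. They sum to 0.9327, so P(stop) = 0.0673. The plan prints 7%.
- q = 0.35: the terms are 0.00018, 0.00195, 0.00998, 0.03226, 0.07382 and 0.12720. They sum to 0.2454, so P(stop) = 0.7546. The plan prints 76%, within one point.

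**Step 2: the middle figure.**
- q = 0.25: the terms are 0.00317, 0.02114, 0.06695, 0.13390, 0.18969 and 0.20233. They sum to 0.6172, so P(stop) = 0.3828. The plan prints 23%.
- Difference: 38.3 − 23 = 15.3 points. Ratio: 38.3 / 23 = 1.66.

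**Step 3: could another reading give 23%?**

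| Calculation | PFS 85% | PFS 75% | PFS 65% |
|---|---|---|---|
| Plan as printed | 7% | 23% | 76% |
| Exact binomial, 6 of 20 | 6.7% | 38.3% | 75.5% |
| 6 of 20, normal approximation with continuity correction | 5.9% | 39.8% | 75.9% |
| 6 of 20, normal approximation without correction | 3.0% | 30.3% | 68.0% |
| 6 of 20, Poisson | 8.4% | 38.4% | 69.9% |
| Exact binomial, 7 of 20 | 2.2% | 21.4% | 58.3% |
| Exact binomial, 6 of 17 | 3.2% | 23.5% | 58.0% |

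The last two rows come near 23% in the middle but lose both outer figures.

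Across every sample size from 6 to 79 and every threshold, only 6 of 20 gives both 7% at 85% PFS and 76% at 65% PFS to within one point. The design closest to all three printed figures is 10 of 32 (1.6%, 26.3% and 73.2%), which still misses by up to 5.4 points and is not the stated sample size.

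**Step 4: incomplete follow-up.** Trials were simulated with entry at 4 or 6 patients per year, exponential or Weibull (shape 1.5) failure times, and a data cut-off 0 to 3 years after the last entry. The failure-time shapes and cut-offs are assumptions. Shorter follow-up lowers all three probabilities together. The settings nearest 23% at 75% PFS give about 1.5% to 3.4% at 85% PFS and 43% to 60% at 65% PFS.

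**Step 5: what 23% would correspond to.** Solving P(X ≥ 6 | n = 20, q) = 0.23 gives q = 0.210, a true PFS of about 79%.

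**The case against.** The arithmetic is not in dispute. Four points can be made against the weight placed on it.

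1. *The method is inferred.* The exact value at 65% PFS is 75.46%, which rounds to 75%, not 76%. The continuity-corrected normal value (75.9%) fits better there but worse at 85% PFS (5.9% against 7%). So no method tried matches both outer figures to the printed digit. This stands as a limit on certainty about the method. It does not help the 23%, since both methods give 38% to 40% at 75% PFS.

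2. *Stopping could mean halting enrolment.* Section 13.0 also allows removal from study, and Section 14.0 does not say how removed patients count. In a simulation with random entry at 6 per year and exponential failure times (an assumption), the sixth failure came before the twentieth enrolment in about 0.4%, 4.5% and 17% of trials at 85%, 75% and 65% PFS. At 4 per year the figures were about 1%, 10% and 33%. So 38% is the chance of ever reaching the boundary, not of cutting accrual short. That qualification stands, but this reading lowers all three figures and moves further from the printed 7% and 76%.

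3. *The PFS label could be the slip.* A PFS of about 79% would give 23%. The documents cannot rule this out. The even 85/75/65 spacing makes 75% the likelier intended value.

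4. *The consequence is modest.* The rule is more protective at 75% PFS than the plan says, and no test, power claim or sample-size argument in Section 14.0 rests on the 23%. This is correct. It limits the seriousness of the error but does not make the figure right.

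**Conclusion.** The concern holds. Under the stated rule and sample size, the chance of stopping at a true 3-year PFS of 75% is about 3 in 8, where the plan says fewer than 1 in 4. The other two printed probabilities are sound to within one point, so the discrepancy is confined to the 75% entry. Where the 23% came from cannot be determined from the documents.

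The result rests on full 3-year assessment of all 20 patients, the same assumption under which the other two figures reproduce. Because one cumulative count is used, the timing of looks does not change the chance of eventually reaching the boundary under that assumption.

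This should be corrected because it misstates an operating characteristic of the only stopping rule. It is not a flaw in the design.

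**What to change.** In Section 14.0, replace 23% with 38%. If 23% was intended, state the method and assumptions that produce it, or correct the PFS value it is attached to. It would help to recompute all three probabilities together and add a phrase naming the method (exact binomial, all 20 patients followed to 3 years); the 65% entry would then read 75%.

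The necessary cost is one number in one sentence. The boundary, the sample size and the 7% figure at 85% PFS do not change.

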15.2 RANDOMIZATION

Not applicable.

16.0 DATA MANAGEMENT ISSUES

A Research Study Assistant (RSA) will be assigned to the study. His or her responsibilities will include data collection, abstraction and entry into CRDB, monitoring of compliance, and data reporting.

16.1 QUALITY ASSURANCE

Registration reports will be generated by the RSA on a regular basis to monitor patient accruals and completeness of the registration data. Routine data quality reports will be generated to assess missing data and inconsistencies. Accrual rates

and extent and accuracy of evaluations and follow-up will be monitored periodically throughout the study period.

17.0 PROTECTION OF HUMAN SUBJECTS

Most patients on this study will be children, adolescents, and young adults, due to the nature of this tumor type. Patients of both sexes and all ethnic backgrounds are eligible for the study. Participation will be voluntary. Potential benefits include comparable event-free survival with hypothesized decreased risk of long-term side effects (neuropsychological, neuroendocrine, audiometric, growth). Alternatives include external beam radiation therapy alone (3600 cGy craniospinal with posterior fossa boost) or reduced-dose radiation therapy (2340 craniospinal with posterior fossa boost) with the same chemotherapy that will be prescribed in this study.

Patients are responsible for all costs of their care including (but not limited to) physician visits, hospitalizations, medications (except for the 3F8 antibody), MRI scans, and laboratory work (except for dosimetry studies).

Patient confidentiality will be protected, but records may be reviewed by appropriate staff of the Memorial Sloan-Kettering Cancer Center or the Food and Drug Administration (FDA).

17.1 Privacy

It is the responsibility of the Research Staff to ensure that Memorial Sloan-Kettering Cancer Center has on file a written acknowledgment of receipt by the subject of the Center's Notice of Privacy Practices. If the subject has not already done so, he/she must sign such an acknowledgment before participating in this study.

MSKCC's Privacy Office may allow the use and disclosure of protected health information pursuant to a completed and signed Research Authorization form. The use and disclosure of protected health information will be limited to the individuals described in the Research Authorization form. A Research Authorization form must be completed by the Principal Investigator and approved by the IRB and Privacy Board.

17.2 Serious Adverse Event (SAE) Reporting

Any SAE must be reported to the IRB as soon as possible but no later than 5 calendar days. The IRB requires a Clinical Research Database (CRDB) AE report to be delivered to the Institutional SAE Manager ([name]) containing the following information:

Fields populated from the CRDB:

- Subject's name (generate the report with only initials if it will be sent outside of MSKCC)
- Medical record number

IRB
PB

Amended: 2/26/08

- Disease/histology (if applicable)
- Protocol number and title

Data needing to be entered:

- The date the adverse event occurred
- The adverse event
- Relationship of the adverse event to the treatment (drug, device, or intervention)
- If the AE was expected
- The severity of the AE
- The intervention
- Detailed text that includes the following information:
 - A explanation of how the AE was handled
 - A description of the subject's condition
 - Indication if the subject remains on the study
 - If an amendment will need to be made to the protocol and/or consent form

The PI's signature and the date it was signed are required on the completed report.

For IND/IDE protocols:

The CRDB AE report should be completed as above and the FDA assigned IND/IDE number written at the top of the report. The report will be forwarded to the FDA by the Institutional SAE Manager through the IND Office.

